3 INTRODUCTION

3.1 Background

Dementia with Lewy bodies (DLB) is one of the most common causes of dementia. DLB, together with Parkinson's disease dementia (PDD), is a form of Lewy body dementia (LBD). Approximately 1.4 million Americans suffer from LBD, making it the second most common cause of neurodegenerative dementia after Alzheimer's disease (AD). In addition to progressive dementia and motor deficits, patients with DLB endure a wide range of debilitating symptoms including cognitive fluctuations, recurrent visual hallucinations, and rapid-eye movement sleep behavior disorder. DLB patients have a short lifespan and rapid cognitive decline compared to AD and PDD patients. As a result, DLB is also associated with greater healthcare costs and caregiver burden than other forms of dementia. Unfortunately, no treatments are available to cure or slow the progression of DLB, making disease-modifying therapies for DLB a critical unmet medical need (Goldman 2020).

A hallmark of DLB is the accumulation of abnormal protein aggregates called Lewy bodies. Lewy bodies are primarily composed of α -synuclein fibrils and oligomers. Although the processes by which these aggregates form and spread through the brain are poorly understood, it is widely thought that the accumulation of α -synuclein is linked to synaptic dysfunction, neurodegeneration, and neuronal death.

Amyloid β ($A\beta$) is also linked to cognitive decline and markers of neurodegeneration in persons with DLB. While synucleinopathy is the defining feature of LBDs, amyloid plaques characteristic of AD are associated with the cognitive impairment in DLB. Approximately 80% of patients suffering from DLB have significant concentrations of $A\beta$ -rich plaque deposits in their brains, in addition to α -synuclein pathology, at autopsy $A\beta$ deposition correlates with cortical thinning, the severity of neurofibrillary tangles, and Lewy body inclusions. The combination of $A\beta$ and α -synuclein deposition in PDD patients is associated with a shorter interval between development of dementia and onset of motor symptoms, as well as a shorter life span. $A\beta$ deposition was linked to cognitive impairment in patients with DLB and PDD. Thus, $A\beta$ -targeted therapies could limit cognitive decline in individuals with DLB.

The Sponsor (Cognition Therapeutics, Inc. [CogRx]) is developing CT1812, a first-in-class brain-penetrant small molecule that selectively clears toxic $A\beta$ oligomers from the brain. CT1812 was identified through a phenotypic screening approach, in which it demonstrated an ability to prevent the binding and effects of $A\beta$ oligomers ($A\beta$ O) on mature neurons in culture (Izzo et al., 2014a; Izzo et al., 2014b). It displaces $A\beta$ O bound to neuronal receptors at synapses and protects

CONFIDENTIAL AND PROPRIETARY

synapses from toxic A β O effects. CT1812 accomplishes this by allosterically modulating a key protein regulator of oligomer receptors, the sigma-2 receptor complex, thus destabilizing the oligomer binding site and increasing the off-rate of A β O, which are then cleared into the cerebrospinal fluid (CSF). By inhibiting oligomer binding, CT1812 blocks downstream synaptotoxicity and restores memory to normal in aged transgenic mouse models of AD.

The sigma-2 receptor complex protein PGRMC1 also binds to α -synuclein monomer and oligomer in synaptosomes. Evidence suggests that α -synuclein oligomers (α -synO) are toxic to synaptic function and the process of autophagy, a vital cellular damage response mechanism. Importantly, CT1812 partially attenuates α -synO binding and internalization. By displacing both α -synO and A β O from neurons, CT1812 may relieve the synaptotoxic effects of these oligomers in DLB patients and is therefore a clinical candidate for this disease.

CT1812 is currently in clinical development for the treatment of AD. CT1812 has been demonstrated to be generally safe and well tolerated in Phase 1 trials in healthy volunteers (NCT02570997) and AD patients (NCT02907567). When administered once daily for 28 days to mild to moderate AD patients, CT1812 significantly reduces concentrations of synaptic degeneration markers in AD patient CSF (NCT02907567). The CT1812 mechanism of action has the potential to halt or slow cognitive decline, which will significantly alleviate the suffering of patients. This hypothesis is being tested in an ongoing six-month trial in mild to moderate AD patients (NCT03507790). The proposed clinical study in DLB patients will leverage these ongoing development efforts for AD and provide an opportunity to investigate a novel therapeutic candidate in an indication for which no disease-modifying treatments exist.

3.2 Nonclinical Experience

3.2.1 Nonclinical Pharmacology Studies

CT1812 is a lipophilic isoindoline formulated as a fumarate salt and is the result of a structure-based medicinal chemistry optimization program comprised of over 300 analogs. CT1812's properties are fully described along with all preclinical studies in the Investigator Brochure. CT1812 has a high affinity at the target receptor sigma-2/PGRMC1 (S2) and is >100-fold selective for this receptor over other receptors and ion channels. Dose-limiting toxicities at higher doses in both species appear to be hypercalcemia and renal tubular damage, both of which are non-invasively monitored via measurement of serum calcium and urinary markers of renal tubular injury such as kidney injury molecule 1 (KIM-149,50).

In vitro pharmacodynamic (PD) studies confirmed CT1812 target binding specificity, affinity and engagement, including the prevention and reversal of A β oligomer binding and the prevention of A β oligomer-induced synapse loss.

In vivo PD studies confirmed the desired consequences of target engagement, including cognitive improvements in an aged transgenic mouse model of AD following oral administration of an apparently tolerated dose of CT1812 daily for 9 weeks. Additional *in vivo* PD studies, using an A β oligomer detecting microelectrode in an aged transgenic mouse model of AD, demonstrated that administration of CT1812 caused an acute increase in soluble A β oligomers in the interstitial fluid of the hippocampus and a sustained increase in soluble A β oligomers in the CSF of the lateral ventricle of the brain. These increases in soluble A β oligomers occurred without a change in the amount of soluble A β 1-40, indicating that displacement of A β oligomers occurred following treatment with CT1812.

3.2.2 Nonclinical Pharmacokinetic Studies

Absorption of CT1812 following oral gavage administration to mice, rats and dogs appears to be very rapid, with brain concentrations exceeding those concurrently measured in plasma. The drug is highly protein-bound in plasma from rat, mouse, dog, and human, but only weakly bound to blood cells. Systemic exposures to CT1812 following oral administration to rats and dogs were greater than dose-proportional at high, toxicologically relevant dosages. Extensive first-pass metabolism appears to be via oxidation and/or direct glucuronidation.

Studies with human recombinant cytochrome P450 (CYP) isoforms show rapid metabolism ($t_{1/2}$ of 6.8 min) by CYP3A4, and slower metabolism ($t_{1/2}$ of 57 and 81 minutes) by CYP2D6 and CYP2C19. A direct glucuronide conjugate was also observed *in vitro* in human hepatocyte incubations, consistent with that observed *in vivo* in rats and dogs.

CT1812 was not an inhibitor of CYP1A2, CYP2B6, or CYP2C8, with less than 50% inhibition of activity observed at the highest concentration evaluated (10 μ M). CT1812 was a weak inhibitor of CYP2C9, CYP2C19, CYP2D6, and CYP3A4, with IC₅₀ values ranging from 4.4 to 38 μ M. However, when evaluated in the context of systemic exposure data in humans, the drug-drug interaction liability from these effects was considered to be minimal. CT1812 was found to be an inducer of CYP3A4 (\geq 0.3 μ M), suggesting a potentially clinically significant risk of drug-drug interactions with this isoform, but induction of CYP2B6 and CYP1A2 appear less likely. CT1812 does appear to be a substrate for p-glycoprotein (P-gp), and inhibits P-gp with an IC₅₀ of 10 μ M. This is considered to be potentially clinically significant, primarily due to the possibility of interactions in the gastrointestinal (GI) tract. *In vitro* inhibition of the OATP1B1 transporter (IC₅₀

of 11.5 μM) by CT1812 does not appear to be clinically relevant, when evaluated in the context of systemic exposure data in humans. As assessed per the FDA 2012 draft guidance for drug-drug interaction (DDI) evaluations, clinically relevant DDI are suggested via CT1812 effects on CYP3A4 and P-gp.

3.2.3 Nonclinical Safety Studies

Two hERG (human Ether-à-go-go Related Gene) assays were performed to assess effects of CT1812 on the rapidly activating delayed rectifier potassium channels (IKr) using channels stably transfected and over-expressed in Chinese Hamster Ovary cells. Using whole-cell patch clamp electrophysiology, CT1812 was tested in both studies in duplicate at concentrations of 1, 3, 10, and 30 mM. Mean IC_{50} values of 26 mM and 0.6 mM were determined in the first and second assay, respectively. Reasons for the differing results are unknown. However, no ECG effects were noted in the telemeterized dog cardiovascular safety study or in the multiple-dose dog pivotal toxicology study when tested up to high-dose mean C_{max} values of approximately 4 μM .

Safety pharmacology studies with rats revealed no apparent effects on CNS or pulmonary parameters following single oral dosages that exceeded the maximum tolerated dose in this species.

General toxicology studies with rats and dogs following oral dosing of CT1812 revealed dose-limiting toxicity that manifested as degenerative changes in the proximal tubules of kidney, hypercalcemia, and vascular mineralization and/or degeneration involving multiple tissues and organs in each species. Tolerable and intolerable dosages and exposures, characterized with each species, informed the selection of dosages for this trial.

Additionally, toxicology studies revealed several test article-related clinical laboratory changes, including elevated serum creatinine and/or BUN that correlated with mild weight loss, elevated serum calcium and reduced urinary specific gravity. The exact mechanism for these changes cannot be determined from those studies. Serum and urine tests will be performed in this trial to evaluate the effect of study drug administration on renal function (including serum creatinine, serum calcium, urine calcium).

Genetic toxicology studies revealed no positive responses in bacterial and mammalian in vitro assays, or in an in vivo mouse bone marrow micronucleus assay when tested up to maximally feasible dosages.

3.3 Clinical Experience

CT1812 has been administered safely with good tolerability in over 60 healthy volunteers in a placebo-controlled Phase 1a trial (COG0101). Six single (10-1120 mg) and three multiple dose cohorts (QD, 14 days, 280-840 mg) were observed under close inpatient stay (N=6-8 treated, 2 placebo per cohort). Plasma concentrations of drug were shown to be approximately dose proportional across two orders of magnitude [0.13-14.93 mg (free base equivalent)/kg], and accumulation was minimal. Peak concentrations of CT1812 were reached within 1 to 2 hours and the plasma half-life was shown to be approximately 12 hours. Adverse events were mostly mild to moderate in severity and principally included headache, nausea, vomiting, diarrhea, constipation, abdominal pain, dyspepsia, upper respiratory tract infection, lightheadedness, syncope, myalgia, dizziness, rash and pain at the lumbar puncture site in those subjects who had lumbar punctures. There was only one AE of severe intensity, being an SAE of upper respiratory tract infection, occurring in one subject in the 840 mg dose of the MAD study, believed to be unrelated to study drug based on a similar pattern of URTIs in subjects receiving drugs other than CT1812 in the study unit during the same time period. One subject in the multiple dose cohort study developed a rash while on study drug. This subject showed improvement after discontinuing CT1812.

No evidence of renal toxicity was observed based on routine measures of renal function (serum creatinine, BUN) or cystatin C.

Four subjects in the MAD study showed an increase in liver function tests below 3X the upper limit of normal (including one subject on placebo). Subsequent studies will closely monitor liver enzyme parameters to determine if these were sporadic findings or possibly drug related.

A fed cohort (280 mg) single dose was compared to the fasting cohort of 280 mg and no significant food effect was observed. A multiple dose cohort of elderly (≥ 65 years old) healthy volunteers was dosed at 560 mg x 14 days, and their exposures were similar to the 840 mg younger healthy volunteer subjects.

In COG0103 15 healthy volunteers evaluated potential effects of CT1812 on the disposition of sensitive substrates of selected CYP isoenzymes CYP2C19 (omeprazole), CYP2C9 (tolbutamide), CYP2D6 (dextromethorphan), and CYP3A4/5 (midazolam). Subjects were administered the probe drugs on Day -2 and PK evaluations performed. On Days 1 through 6, each subject took CT1812 560 mg. The CT1812 dose on Day 6 was taken concomitantly with the probe drug cocktail, and PK evaluation was conducted. No significant interaction was observed for isoenzymes 2C19 and 2C9. A weak drug interaction was observed between steady-state

Protocol # COG1201
Version # 3.0 Issue Date 20 Sep 2022

CT1812 in DLB

CT1812 and midazolam 4 mg (CYP3A4). Midazolam AUC_{last} and the AUC_{last} ratio (parent to metabolite) decreased by 24% and 28%, respectively, when midazolam 4 mg was taken with steady state CT1812 than when midazolam was taken alone. A weak drug interaction was observed between steady-state CT1812 and dextromethorphan 50 mg (CYP2D6), as indicated by a 1.75-fold and 2-fold increase in dextromethorphan AUC_{last} and C_{max}, respectively, following the combination treatment relative to dextromethorphan alone; however, the dextromethorphan/dextrophan AUC_{last} ratio was similar between treatments. Based on the small magnitude of the interactions observed in this study for the isoenzymes CYP2D6 and CYP3A4, clinically meaningful implications are unlikely.

A Phase 1a/2 trial (COG0102), evaluated the safety and pharmacokinetics of three doses of once-a-day CT1812 (90 mg, 280 mg, 560 mg) dosed for 28 days in subjects with mild to moderate Alzheimer's disease. This study enrolled 19 subjects in a 1:1:1:1 ratio of these doses vs. placebo. In general, all doses were relatively well tolerated, with no SAEs. All AEs were considered mild or moderate. While there was an increased frequency observed in total AEs with increasing dose, the small number of treated subjects does not permit definitive conclusions regarding the incidence of AEs by dose in a larger study population. Specific AEs which were noted to occur with greater frequency at the 560 mg dose included transient lymphocytopenia, nausea, vomiting, headache, fatigue, and depression. These AEs resolved in most instances while treatment was ongoing; one subject at the 560 mg dose experienced an ALT increase of 4.7 X ULN which resolved to normal levels after discontinuation of study drug. Cognitive outcomes were similar across the treatment groups. Plasma CT1812 concentration increased approximately dose proportionally, with a dose dependent increase in CSF concentration. CSF concentrations at all tested doses were > 80% of estimated brain PGRMC-1 receptor occupancy, which was the threshold associated with efficacy in preclinical studies.

A Phase 1 trial (COG0105) was a pilot study of Synaptic Vesicle Glycoprotein 2A (SV2A) PET ligand ¹¹C-UCB-J to evaluate the effect of CT1812 treatment on synaptic density in subjects with Mild to Moderate Alzheimer's Disease. Eligible subjects were randomized in a 1:1:1 (300 mg CT1812: 100 mg CT1812: placebo) ratio. This was a 24-week treatment period, with an optional 24-week double blind extension period which was instituted after study startup; 23 subjects were dosed, 18 completed the original trial, and 13 rolled over to the double-blind extension.

Overall, CT1812 was generally well tolerated when delivered daily over a 24- or 48-week period in subjects with mild to moderate AD.

The most common TEAE in the CT1812 treatment arms was headache. Two subjects were withdrawn from the study due to TEAEs of liver function test increased (mild, probably related to

study treatment). In the CT1812 100 mg arm, two cases of post-dose neurological examination findings were assessed as clinically significant for coordination (bilateral ideomotor apraxia) and mental state (presence of delusions). There were 2 subjects (CT1812 100 mg and 300 mg treatment arms) with suicidal ideation as assessed by the C-SSRS.

A Phase 1 trial (COG0104) was a pilot study to evaluate the effect of CT1812 treatment on A β oligomer displacement into CSF in subjects with Mild to Moderate Alzheimer's Disease. Subjects were randomized to CT1812 560 mg/280 mg or placebo in a 1:1 ratio. A single dose was administered following insertion of an indwelling CSF lumbar catheter, and hourly CSF and plasma sampling was performed over a period of 24 hours to assess for oligomer displacement.

Overall, CT1812 was generally well tolerated in mild to moderate AD patients when delivered as a single dose of 560 mg.

There are several ongoing studies. COG0201 is a Phase 2 randomized, 6 month double-blind, placebo-controlled, parallel-group, study to evaluate the safety and efficacy of CT1812 in subjects with mild to moderate Alzheimer's disease with a target enrollment of 120 subjects. Subjects are randomized to one of three treatment arms (CT1812 at doses of 100 or 300 mg/d or placebo, n=40/group). To date 62 subjects have randomized. There have been several episodes of LFT elevation at various timepoints that have resolved following drug discontinuation or spontaneously. No SAEs have been considered drug-related.

COG0202 is a Phase 2 randomized, double-blind, placebo-controlled electroencephalography (EEG) study to evaluate the Effect of CT1812 Treatment on Synaptic Activity in Subjects with Mild to Moderate Alzheimer's Disease. This is a single-site, 16 subject, 29-day, 2-period crossover Phase 2 study of 1 dose level of CT1812 (300 mg) or placebo randomized in a 1:1 ratio. The purpose is to evaluate the efficacy of CT1812 in restoring synaptic function in subjects with mild to moderate Alzheimer's disease (AD) through quantitative EEG measurements, as reflected by relative theta power.

3.4 Rationale for Study

CT1812 was shown to be safe and well tolerated in a study of healthy volunteers and in Phase 1 studies of subjects with mild to moderate Alzheimer's disease. This Phase 2 study is designed to evaluate the safety of two doses of CT1812 administered once daily for 6 months in adults aged 50 to 85 who have been diagnosed with mild to moderate DLB (the targeted clinical indication for CT1812). Randomized subjects will receive 100 mg of CT1812, 300 mg of CT1812, or placebo once daily for 182 days. Exploratory endpoints that evaluate the effect of CT1812 on biomarkers

and potential change in α -synuclein pathology in skin biopsies over the course of 6-months are also included.

3.5 Rationale for Selected Doses

Based on brain receptor occupancy studies in animals, the daily dose of 300 mg/day is projected to exceed 95% occupancy while the 100 mg/day dose is projected to exceed 80% receptor occupancy. In the Phase 1 multiple dose 2-week trial, doses exceeding 300 mg/day were well-tolerated in both younger (≤ 64 years of age) and older (≥ 65 years of age) subjects. Transient increases in LFTs were noted in some subjects. Subjects were discontinued and LFTs returned to normal after discontinuation. In the phase 1 AD trial tolerability was also acceptable with no severe or serious adverse events observed at doses exceeding 300 mg/day.

4 STUDY OBJECTIVES

4.1 Primary Objectives

- To assess the safety and tolerability of CT1812 as a treatment for mild to moderate Dementia with Lewy Bodies.

4.2 Secondary Objectives

- To assess exploratory measures of efficacy at baseline, 3 months, and 6 months.
- To assess pharmacodynamic target engagement and potential biomarker evidence of disease modification.

4.3 Exploratory Objectives

- To evaluate the efficacy of two doses of once-daily oral CT1812, administered for 6 - months in subjects with Dementia with Lewy Bodies.

5 STUDY TYPE AND DESIGN

5.1 Study Type

This is a multi-center, randomized, double-blind, placebo-controlled, study of 120 subjects with three dose arms: 100 mg/day and 300 mg/day of CT1812, vs placebo.

5.2 Endpoints

5.2.1 Safety Endpoints

- The incidence and severity of adverse events.
- The change in usage of concomitant medications.
- Changes in vital signs.
- Changes in physical exam findings.
- Changes in electrocardiogram findings.
- Changes in clinical laboratory testing (serum chemistry, hematology, urinalysis).
- Changes in the Columbia Suicide Severity Rating Scale (C-SSRS).

5.2.2 Efficacy Endpoints

- Montreal Cognitive Assessment Scale (MoCA)
- Epworth Sleepiness Scale (ESS)
- Clinician Assessment of Fluctuation (CAF)
- ADCS-Clinical Global Impression of Change (CGIC).
- ADCS-Activities of Daily Living (ADCS-ADL).
- Movement Disorder Society – United Parkinson's Disease Rating Scale Part III (MDS-UPDRS Part III)
- Cognitive Drug Research Battery (CDR)
- Neuropsychiatric Inventory (NPI)

5.2.3 Pharmacokinetic/Pharmacodynamic Endpoints

- **Pharmacokinetics:**
 - CT1812 CSF/plasma concentration ratio (end of study only).
 - Changes in pre-dose CT1812 plasma concentrations.
- **Pharmacodynamics:**
 - Plasma - A β , phospho-tau, α -synuclein, phospho- α -synuclein, α -synuclein oligomers. Other exploratory biomarkers may also be evaluated.
 - Optional CSF- A β , tau, phospho-tau, neurogranin, synaptotagmin, SNAP25 (synaptosomal-associated protein 25), Neuro Filament Light Chain (NFL), A β oligomers, α -synuclein, phospho- α -synuclein, α -synuclein oligomers. Other exploratory biomarkers may also be evaluated.

5.3 Study Design

This is a multi-center, randomized, double-blind, placebo-controlled, study of 120 subjects has three dose arms: 100 mg/day and 300 mg/day of CT1812, vs placebo.

Subjects will be screened for eligibility by physical, laboratory, psychometric and neurologic examinations, and neuroimaging. Subjects may opt into collection of pre-dose CSF. If a subject opts into CSF collection, this is to be completed along with screening procedures \leq 42 days prior to randomization at Baseline/Day 1. After having met all inclusion criteria, and none of the exclusion criteria, subjects will be randomized equally to one of three treatment arms (CT1812 at doses of 100 mg/day, 300 mg/day or placebo, up to n=40 group). On clinic visit days, study drug will be taken in the clinic after all baseline procedures been conducted. On days where there are no clinic visits, subjects will take study drug each morning at home. Subjects and their caregivers/study partner will return to the clinic for repeat psychometric/neurologic testing, safety procedures and PK and PD sample collection at the intervals described below.

- Subjects will return to the clinic approximately every 2 weeks after their baseline visit until Day 70, then every four weeks until Day 182 (See Table 1). A safety follow-up visit will occur approximately 28 days after the end of treatment for all subjects that complete through Day 182.

Subjects who prematurely discontinue the study for any reason will be asked to attend an early termination visit within 2 weeks of the last dose of study drug.

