Serial monitoring of ALT/AST/bilirubin and INR will be performed, initially with repeat values within 4 days of discontinuation of study drug. If LFTs are still elevated 4 days post-study drug interruption, participants should have LFTs checked again 4 days later (+/- 1 day). The site investigator and medical monitor should agree to a plan for further LFT monitoring depending on whether the LFTs are still increasing or trending towards normal. Repeat testing should be carried out until LFTs have normalized. The LFTs in this instance can also be run locally for more rapid turnaround.

In the event a reversible etiology is found to explain the elevated liver enzymes (such as a common bile duct stone), drug may be restarted following normalization of LFTs, and after discussion between the Medical Monitor and site PI.

Study drug will be temporarily discontinued if a participant does not achieve the aforementioned levels of elevated LFTs but has an elevation of ALT or AST $>3 \times$ ULN. These participants will have LFTs retested within 4 days after their last dose of study drug. If LFTs are still elevated 4 days post-study drug interruption, participants will have LFTs checked again 4 days later (± 1 day), and the site PI and medical monitor will agree to a plan for further monitoring of the findings. The LFTs in this instance can also be run locally for more rapid turnaround.

LFTs do not need to be intensively monitored when ALT and AST are $\leq 3 \times$ ULN with no elevation of bilirubin, however the investigator and the medical monitor will formulate a plan for serial testing of LFTs. Cessation of dosing is not required in this circumstance but may be temporarily interrupted at the discretion of the investigator.

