8.4 Withdrawal of Subjects

A subject should be withdrawn from the study if any of the following occur:

- 1) Withdrawal of subject consent.
- 2) Investigator determines that withdrawal from the study is in the best interest of the subject.
- 3) Major protocol violation (i.e., circumstances where confounding conditions make it impossible to derive sound scientific or medical conclusions from the primary endpoint data generated on a subject).
- 4) Any condition, injury, or disease that becomes apparent during the study and necessitates the termination of the subject from the study; including events detailed in Section 6.3.1- Safety Stopping Rules.
- 5) Administrative reason (e.g., termination of the clinical study by a Regulatory Agency or the Sponsor).

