8.5 Subject Withdrawal Procedures

8.5.1 Follow-up Procedures for Subjects Who Withdraw Prematurely

The date and the reason for study drug discontinuation or subject withdrawal from the study must be recorded on the Case Report Form. If the subject has received one or more doses of study

Protocol # COG1201
Version # 3.0 Issue Date 20 Sep 2022

CT1812 in DLB

drug, and has not withdrawn consent, the subject shall return for the Early Termination Visit. The Early Termination Visit will occur within 2 weeks of the last dose.

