9.2.11 Visit 11 Study Day 182 / Early Termination

The subject will return to the clinic.

- Within the -2-day window for scheduling assessments:
- If the subject opted into the lumbar puncture, perform lumbar puncture, and collect CSF a minimum of 24 hours before the Day 182 / Early Termination Visit
- The subject should undergo the Syn-One Test™ skin biopsy at least 24 hours prior to the Day 182 / Early Termination Visit

Pre-dose Assessments:

- Administer MOCA, CDR, ADCS-ADL, NPI, ADCS-CGIC, MDS-UPDRS Part III, CAF and ESS
- Administer C-SSRS Since Last Visit version

- Perform complete physical examination with neurological examination
- Measure and record vital signs
- Draw blood and prepare sample for serum chemistry and hematology. Blood should be drawn within an hour of urine collection.
- Collect blood samples for PK and exploratory biomarker analysis
- Collect urine samples for urinalysis
- Record any AEs
- Record changes in medications
- Conduct drug accountability) and collect all remaining drug from subject
- Administer last dose of study drug with food

Post-dose Assessments

- Record ECG ~1-2 hours post-dose
- Instruct subject to return for Day 210, safety follow up visit

Any subject that discontinues prematurely should complete Visit 11/Day 182 as an Early Termination visit. For subjects prematurely discontinuing, an early termination visit should be scheduled within 2 weeks of the last dose of study medication. If early termination visit is 3 or more days from the last dose, PK sampling should not be done. The remainder of the assessments below should be performed.

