13.1.1 Serious Adverse Event Reporting by the Investigator to the Sponsor

Any SAE that occurs after a subject has entered the study, whether related to study drug or not, must be reported to the CRO immediately (within 24 hours) via e-mail at the address noted below. A completed Serious Adverse Event Report Form with as much detail as possible must be included with the email. The Investigator must report all SAEs occurring from the time the subject signs the ICF until 30 days after last treatment with the study drug.

Sponsor Representative and Contact Information for SAE Reporting:

[contact]

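### The protocol gives conflicting instructions on who attends the off-drug safety visit after stopping early, and on whether a temporary liver hold means leaving the study

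*Protocol*

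**What the plan says.** **Visits after the last dose.** Protocol 5.3 states "A safety follow-up visit will occur approximately 28 days after the end of treatment for all subjects that complete through Day 182". The synopsis and SAP 4 carry the same restriction. Those who stop early "will be asked to attend an early termination visit within 2 weeks of the last dose of study drug". Section 8.5.1, on premature withdrawal, adds "The Early Termination Visit will occur within 2 weeks of the last dose" and names no later visit.

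Three other places read differently:

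- Section 9.2.11 covers both Day 182 and early termination. It says "Any subject that discontinues prematurely should complete Visit 11/Day 182 as an Early Termination visit", and its post-dose list includes "Instruct subject to return for Day 210, safety follow up visit".
- Table 1 gives Visit 12 two anchors: Day 210, and 30 days after treatment.
- Section 12.2.2 collects adverse events from consent up to a Follow-up Visit, which early stoppers do not have under 5.3.

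**Reporting windows.** Section 13.1.1 requires SAE reports "until 30 days after last treatment with the study drug". Section 12.2.3 has sites track open events at least weekly after early withdrawal, for up to 30 days. It asks subjects to report new events for 30 days, and it follows any adverse event or clinically significant laboratory abnormality until normal or acceptable.

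**Liver rules and withdrawal.** Section 8.4 item 4 withdraws a subject from the study for a condition that requires it, "including events detailed in Section 6.3.1- Safety Stopping Rules". Section 6.3.1 has two tiers. Subjects meeting any of three upper-tier criteria receive no more drug, except that where a reversible cause is found "drug may be restarted following normalization of LFTs, and after discussion between the Medical Monitor and site PI". Subjects with ALT or AST above 3 × ULN who do not meet those criteria have drug stopped temporarily.

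**Analysis.** Protocol 12.2.1 ends the treatment period, and with it treatment emergence, at the last dose. SAP 15.1 counts any event on or after the first dose and gives no end date. SAP 10.4 puts early termination data from before Day 170 in listings only and imputes nothing.

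**The concern.** Safety is the primary objective. Subjects who stop early include those who stop because of an adverse event, so a site needs to know whether they return for off-drug laboratory tests and a C-SSRS, and when. The passages give different answers. A site following 5.3 would schedule nothing after the exit visit, while a site following 9.2.11 would bring the same subject back at Day 210.

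The second conflict concerns who remains in the study. If a temporary drug hold is treated as a ground for study withdrawal, the subject leaves, has no Month 6 MoCA in the key efficacy comparison, and attends no later visits. LFT rises have been seen with this drug in earlier studies (Protocol 3.3), so such exits could be related to treatment.

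The two meet in the safety tables. With an open-ended TEAE definition, a subject questioned and tested about four weeks off drug has more opportunity to contribute an event than one last seen within two weeks.

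**Working it through.** **1. The plan's own figure.** Synopsis and 7.2: maximum participation 254 days. Screening 42 + Day 210 + 2-day window = 42 + 210 + 2 = 254. This reproduces, and it shows that Day 210 is a fixed study day counted from the first dose.

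**2. Off-drug interval for completers.** Formula: Visit 12 day − Visit 11 day. The last dose is taken at Visit 11 (9.2.11).

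| Source of window | Shortest | Nominal | Longest |
|---|---|---|---|
| Synopsis (182 ± 2, 210 ± 2) | 208 − 184 = 24 | 210 − 182 = 28 | 212 − 180 = 32 |
| Table 1 (182 ± 2, 210 + 2) | 210 − 184 = 26 | 28 | 212 − 180 = 32 |

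**3. Off-drug interval for early stoppers under 5.3 and 8.5.1.** One visit, 0 to 14 days after the last dose. Against the nominal 28 days the scheduled shortfall is 28 − 14 = 14 to 28 − 0 = 28 days. Of the 30-day reporting window, 30 − 14 = 16 to 30 − 0 = 30 days have no scheduled assessment.

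**4. The competing instructions.** For a completer the two Table 1 anchors can both be met: 182 + 30 = 212, the last day of the window. For an early stopper they separate. Illustration, last dose on Day 40:

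| Text followed | Last scheduled contact | Days off drug |
|---|---|---|
| 5.3, 8.5.1, synopsis, SAP 4 | Day 40 to Day 54 | 0 to 14 |
| Table 1 label, 30 days after treatment | 40 + 30 = Day 70 | 30 |
| 9.2.11 list, Day 210 | Day 210 | 210 − 40 = 170 |

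Section 9.2.11 does not settle the matter. The same list includes giving the last dose in clinic, which cannot apply to a subject barred from further dosing under the upper liver tier. It appears to have been written with completers in mind.

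**5. Section 8.4 item 4 against 6.3.1.**

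| 6.3.1 situation | 6.3.1 instruction | 8.4 item 4 read strictly |
|---|---|---|
| Upper tier, no reversible cause | No further drug; monitor | Leave the study |
| Upper tier, reversible cause found | Restart possible once LFTs normalize | Leave the study |
| Lower tier | Temporary stop; retest | Leave the study |

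The second and third rows contradict each other outright. In the first, stopping drug and leaving the study are merged but do not conflict.

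**6. Effect on the analysis.** A subject who leaves before Day 170 contributes no Month 6 MoCA; Day 28 and Month 3 values already collected still enter the MMRM. SAP 9.1 tabulates stopping treatment and leaving the study separately, so the SAP expects a distinction that 8.4 does not make. SAP 16 does not list the TEAE definition among its changes from the protocol.

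**7. Number of subjects.** The sample-size allowance is 120 − 105 = 15, or 15/120 = 12.5%.

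**The case against.** The strongest reply is that early stoppers are not left unobserved. The 30-day SAE window applies to everyone, new events are requested for 30 days after either discharge or early withdrawal, and open events are tracked weekly. Any known adverse event or clinically significant laboratory value is followed until acceptable, and LFTs are repeated until normal. The exit visit also includes a complete physical examination and an ECG, which Day 210 lacks. All of this stands.

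A reader might therefore go too far in four ways:

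- *That early stoppers have the shortest safety follow-up overall, or that those who stop for a safety event are observed least.* The documents do not support this. The shortfall is confined to scheduled detection of findings that are new after the exit visit. The cover for those relies on the subject or caregiver reporting them, and it includes no scheduled creatinine, calcium, urinalysis or C-SSRS.
- *That the Day 210 visit is cleanly withheld from early stoppers.* The 9.2.11 list and the Table 1 label point the other way. It is an inconsistency.
- *That anyone meeting a liver rule must leave the study, and that 6.3.1 is a hold-and-restart rule.* Item 4 is limited to conditions that require termination, and a temporary hold need not. The upper-tier default is no further drug. But item 4 then names the 6.3.1 events as included, without separating tiers, so the strict reading is open to a site.
- *That about 7 of 80 active subjects would exit for liver reasons.* This takes 2 of 23 (8.7%) from the earlier 24-week study and multiplies by 80. The 23 include placebo subjects, the two cases are described as mild, and nothing says they met the 6.3.1 thresholds. The exact 95% interval for 2/23 is 1.1% to 28.0%, or roughly 1 to 22 of 80. No count can be relied on.

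**Conclusion.** The point holds as an inconsistency with a limited but real consequence. On the wording of 5.3, 8.5.1, the synopsis and SAP 4, scheduled laboratory, urinalysis, vital sign and C-SSRS checks reach 0–14 days off drug for early stoppers and 24–32 days for completers (26–32 with the Table 1 window). On other text in the same protocol, an early stopper would return at 30 days after treatment or at Day 210. A site cannot tell which applies.

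Section 8.4 item 4 and 6.3.1 conflict for the temporary hold and for the conditional restart. Loss of the Month 6 MoCA for a subject on hold depends on the strict reading of item 4 and on exit before Day 170.

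A reader might infer that the arm comparison of TEAEs is biased. That would need early stopping to differ by arm, which the documents do not establish. What they do show is that the SAP definition allows unequal off-drug observation to enter the tables, whereas the protocol definition, ending at the last dose, does not.

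The figure of about 15 subjects assumes that dropout equals the sample-size allowance. No view is given on which follow-up or liver rule is clinically right.

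**What to change.** 1. Reconcile the synopsis, 5.3, 8.5.1, 9.2.11–9.2.12, Table 1 and SAP 4 so that they state one rule: who attends Visit 12, whether this includes subjects who stop early, and from what anchor it is timed. Make the end of adverse event collection in 12.2.2 match.
2. Reconcile 8.4 item 4 with the tiers of 6.3.1, and define stopping study drug separately from leaving the study, as the SAP disposition tables already do. The sponsor's clinical team should decide which rule applies in each tier.
3. Align the TEAE definitions in Protocol 12.2.1 and SAP 15.1 on one window relative to the last dose, common to all subjects, and record any change in SAP 16.

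The cost is amendment and SAP wording. If the sponsor decides that Visit 12 applies to early stoppers, it adds about 15 attendances at an already defined visit (120 − 105), with the burden that places on subjects who are off drug.
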